4.2. Exclusion Criteria

There are no exclusion criteria for participating in this study.

4.3. Randomization Criteria

Not applicable.

4.4. Lifestyle Guidelines

Not applicable.

5. STUDY TREATMENTS

This is an observational study, using enhanced surveillance of infants with potential exposure in-utero whose mother participated in a tanezumab clinical study. There is no active study treatment in this observational study. However, the neonatal/pediatric evaluations should be performed in a blinded fashion (while the mother of the infant is informed as to treatment allocation, the evaluator is not informed to the treatment the infant's mother received).

For the purposes of this study, and per International Conference on Harmonization (ICH) guidelines, investigational product is defined as a pharmaceutical form of an active ingredient or placebo being tested or used as a reference in a clinical trial, including a product with a marketing authorization when used or assembled (formulated or packaged) in a way different from the approved form, or when used for an unapproved indication, or when used to gain further information about an approved use (ICH E6 1.33).

5.1. Allocation to Treatment

Attempts will be made to enroll all cases of EIU irrespective of prior therapy.

5.2. Breaking the Blind

Not applicable.

5.3. Investigational Product Supplies

Not applicable.

5.3.1. Dosage Form(s) and Packaging

Not applicable.

5.3.2. Preparation and Dispensing

Not Applicable.

5.3.3. Administration

Not applicable.

5.4. Compliance

Not applicable.

5.5. Investigational Product Storage and Investigational Product Accountability

Not applicable.

5.6. Concomitant Medications

Not applicable.

5.7. Rescue/Escape/Salvage Therapy

Not applicable.

6. STUDY PROCEDURES

6.1. Screening

There is no screening period for participation in this study. Informed consent must be obtained before any study procedures are conducted.

6.2. Study Period

The enrolled infants will participate from birth to at least the age of 15 months. The planned visits are outlined below. Neonatal/pediatric evaluations should be performed by a designated physician, such as a pediatric neurologist and a clinical psychologist (neurodevelopmental scales) who will be identified by the investigator or Pfizer.

6.2.1. (Visit 1) Newborn (0-2 Months of Age: Birth or at Any Time within 2 Months of Age)

6.2.1.1. History and Physical Examination

Demographic data from the parents (obstetrics history, history of previous children) and estimated date of conception and gestational age at birth should be collected and recorded in a consultation report as provided by the obstetrician or gynecologist to the investigator as well as added to the CRF. Dosing dates with study drug are considered part of the initial protocol where the exposed mother participated but last maternal dosing date should be added to the current CRF.

Consultation reports and overall clinical impression of immediate pre-parturition maternal status provided by an obstetrician/gynecologist or practitioner are to be reported to the investigator. This information is to be maintained as a source document, a de-identified copy of which will be forwarded to the Sponsor within 35 days of receipt/completion.

Consultation reports and overall clinical impression from attending birth physician assessment of delivery difficulty: number/characterizations of any complications as minor or major reported to the investigator. This information is to be maintained as a source document, a de-identified copy of which will be forwarded to the Sponsor within 35 days of receipt/completion. Physical examination to include measurements of occipital-frontal head circumference, length, weight and post-birth age (weeks), and systolic and diastolic blood pressure, pulse rate, respiratory rate and temperature. The examiner will provide a report to the investigator.

6.2.1.2. Neurological Examination (Pediatrician or Pediatric Neurologist)

The neurologic examination will evaluate all cranial nerves except I (smell), IX (taste) and XI (shoulder shrug). Motor examination will include evaluation of muscle tone, bulk and movement. Sensory examination will include test of temperature and superficial pain (homologous dermatomes using cold tuning fork, neurological examination pin) and deep

pain by pressure on Achilles tendon. Reflex evaluation will include biceps, brachioradialis, patellar, and Achilles tendons. Evaluation for persistence of developmental reflexes including Moro reflex, palmar and planter grasp, and tonic neck response will be evaluated. Autonomic nervous system evaluation will include examining pupillary reaction, heart rate changes in response to activity, and inquiring about abnormal sweating.

The pediatrician's or pediatric neurologist's consultation report which describes the outcome of each assessment and overall clinical impression of the pediatric neurological examination will be provided to the investigator.

6.2.2. (Visit 2) 8 Months of Age (Anytime during the 8th Month)

6.2.2.1. Physical Examination

Refer to [History and Physical Examination](#) as described previously.

6.2.2.2. Neurological Examination (Pediatrician or Pediatric Neurologist)

Refer to [Neurological Examination](#) as described previously.

6.2.2.3. Developmental Assessment (Clinical Psychologist)

Developmental assessment (cognitive, social, language, gross and fine motor skills, neurological intactness) is recommended to be performed by a clinical psychologist utilizing the BINS and REEL-3. If a clinical psychologist is unavailable or cannot be readily located, the pediatrician or pediatric neurologist can perform the developmental assessments. The neonatal/pediatric evaluations should be performed in a blinded fashion (the evaluator is not informed to the treatment the infant's mother received).

Manuals for the collection of the BINS and REEL-3 will be provided to the parent protocol site and then forwarded to the relevant expert for data collection at the evaluation.

Consultation reports which describe outcome of each assessment and overall clinical impression from developmental assessment will be provided in a report to the investigator and entered in the CRF. This information is to be maintained as a source document, a de-identified copy of which will be forwarded to the Sponsor within 35 days of receipt/completion. The outcome of the clinical assessment by the psychologist will be reviewed by the investigator and overall clinical impression will be documented in the case report form.

6.2.3. (Visit 3) 15 Months of Age (Anytime during the 15th Month)

Assessments performed at Visit 2 will be repeated at Visit 3 to allow for evaluation of further development of cognitive function and the motor, sensory and autonomic functions.

The need for further neurologic or neurodevelopmental evaluations will be determined at the 15 month visit by the pediatric neurologist, developmental psychologist, or pediatrician and conveyed to the investigator. If there are no outstanding significant adverse events (AEs) present at the 15 month visit, participation in this current protocol will be considered

completed and additional follow up will not be required. See [Section 6.3](#) below for additional details if outstanding significant neurological or neuro-developmental AEs remain.

Submission of consultation reports and overall clinical impression to be submitted as previously described.

6.3. End of Treatment/Follow-up Visit

The need for further physical, neurologic or developmental evaluations will be determined at the 15 month visit by the pediatrician, pediatric neurologist or psychologist and scheduled to occur approximately within a 6 month period as clinically indicated. If there are no outstanding significant neurological or neurodevelopmental adverse events are present at the approximate 6 month follow up visit, participation in this current protocol will be considered completed and additional follow up will not be required. Submission of consultation reports and overall clinical impression to be submitted as previously described.

6.4. Post-study Subject Interview (If Applicable)

The need for additional post-study follow up visits as will be clinically determined subsequent to the Visit 3 (15 month visit) plus approximate 6 month visit as outlined above. Thus, this post-study subject interview period is for continued evaluations approximately every 6 months until the neurological or neurodevelopmental event(s) are considered resolved, or determined to be clinically stable and the case can be closed, up to a maximum of 36 months. Submission of consultation reports and overall clinical impression to be submitted as previously described.

6.5. Subject Withdrawal

Subjects (parents of the infants) may withdraw from the study at any time at their own request, or they may be withdrawn at any time at the discretion of the investigator or sponsor for safety, behavioral, or administrative reasons. If a subject does not return for a scheduled visit, every effort should be made to contact the subject. In any circumstance, every effort should be made to document subject (infant) outcome, if possible. The investigator should inquire about the reason for withdrawal, request the parent/subject return for a final visit, if applicable, and follow-up with the subject regarding any unresolved adverse events.

If the subject (parents of the infant) withdraws from the study, and also withdraws consent for disclosure of future information, no further evaluations should be performed, and no additional data should be collected. The sponsor may retain and continue to use any data collected before such withdrawal of consent.

7. ASSESSMENTS

Every effort should be made to ensure that the protocol-required tests and procedures are completed as described. However, it is anticipated that from time to time there may be circumstances, outside of the control of the investigator, that may make it unfeasible to perform the test. In these cases the investigator will take all steps necessary to ensure the safety and well-being of the subject. When a protocol-required test cannot be performed, the investigator will document the reason for this and any corrective and preventive actions that

he or she has taken to ensure that normal processes are adhered to as soon as possible. The study team will be informed of these incidents in a timely fashion.

The physical and neurological examinations must be performed by a pediatrician or pediatric neurologist with experience in rating neurodevelopment skills in neonates.

Raters for the BINS and REEL-3 scales should have experience in rating neurobehavioral development in pediatrics; a clinical psychology degree is recommended. If a clinical psychologist is unavailable or cannot be readily located, the pediatrician or pediatric neurologist can perform the developmental assessments.

If the subject is seen by another healthcare professional during the follow-up, the investigator should also obtain a report and the information is to be maintained as a source document.

7.1. History and Physical Examination (Performed by a Pediatrician or Pediatric Neurologist)

7.1.1. Physical Examination

Each infant will undergo a physical examination at the three visits. Details of the physical examination can be found in the [Study Period](#) section.

7.2. Neurological Examination

The neurologic examination will be performed by the pediatric neurologist and should assess the mental status, cranial nerves, motor and sensory systems and reflexes of the infant. Details of the neurological examination can be found in the [Study Period](#) section.

7.3. Developmental Assessment (Performed by Pediatrician, Pediatric Neurologist or Clinical Psychologist)

Development assessments (cognitive, social, language, gross, and fine motor skills, neurological intactness) will be performed by a clinical psychologist at Visits 2 and 3 utilizing the BINS and REEL-3. If a clinical psychologist is not available to perform these assessments, then the pediatrician or pediatric neurologist can perform them.

7.3.1. Bayley Infant Neurodevelopmental Screener (BINS)

BINS is a validated instrument designed specifically for a high-risk infant population. It consists of 11-13 items for different age levels that assess cognitive, social, language, gross, and fine motor skills. The BINS also includes items that measure neurological intactness, such as ratings of active and passive tone in the upper and lower extremities, and scoring of quality of movement of the upper and lower extremities. The BINS form is attached in [Appendix 2](#).

7.3.2. Bzoch-League Receptive-Expressive Emergent Language Test (3rd Edition) (REEL-3)

The Receptive-Expressive Emergent Language Test, 3rd edition, is designed to identify infants and toddlers who have language impairments or who have other disabilities that affect language development.¹⁰ The REEL-3 has two core subtests, Receptive Language and Expressive Language, and a supplementary subtest, Inventory of Vocabulary Words. Results are obtained from a caregiver interview.

The REEL-3 is based on a contemporary linguistic model. It includes current studies relating to normative base, reliability, and validity. The normative sample includes 1112 infants and toddlers from around the United States. The demographic characteristics of the sample were matched to those of the United States according to the 2000 census. The normative sample was stratified on the basis of age, gender, race, ethnic group membership, and United States geographic location only. Standard scores, percentile ranks, and age equivalents are provided. The average reliability coefficients for all the test scores are high (exceeding .90). Test/retest studies show that the REEL-3 is stable over time.

The REEL-3 test is attached in [Appendix 3](#).

7.4. Banking Samples

No sample are planned to be collected or banked for exploratory research.

7.5. Suicidality Assessment

Due to the age of the subjects relevant to the current protocol, no suicidality assessments will be obtained.

8. ADVERSE EVENT REPORTING

8.1. Adverse Events

All observed or volunteered SAEs and non-serious neurological or neuro-developmental AEs regardless of treatment group or suspected causal relationship to the investigational product(s) will be reported as described in the following sections. Non-serious, non-neurological AEs will not be collected (See [Appendix 4](#) for additional guidance).

For these SAEs and non-serious neurological or neuro-developmental AEs, the investigator must pursue and obtain information adequate both to determine the outcome of the AE and to assess whether it meets the criteria for classification as a SAE requiring immediate notification to Pfizer or its designated representative. For all SAEs and non-serious neurological or neuro-developmental AEs, sufficient information should be obtained by the investigator to determine the causality of the AE. The investigator is required to assess causality. Follow-up by the investigator may be required until the event or its sequelae resolve or stabilize at a level acceptable to the investigator, and Pfizer concurs with that assessment.

As part of ongoing safety reviews conducted by the sponsor, any nonserious AE that is determined by the sponsor to be serious will be reported by the sponsor as an SAE. To assist in the determination of case seriousness, further information may be requested from the investigator to provide clarity and understanding of the event in the context of the clinical study.

8.2. Reporting Period

For SAEs, the active reporting period to Pfizer or its designated representative begins from the time that the subject (or subject's parent(s)/legal guardian) provides informed consent, through the subject's last visit. Informed consent is obtained prior to the subject's participation in the study, ie, prior to undergoing any study related procedure.

SAEs occurring to a subject after the active reporting period has ended should be reported to the sponsor if the investigator becomes aware of them; at a minimum, all SAEs that the investigator believes have at least a reasonable possibility of being related to investigational product are to be reported to the sponsor.

For non-serious neurological or neuro-developmental AEs, the reporting period to Pfizer or its designated representative begins from the time that the subject (or subject's parent(s)/legal guardian) provides informed consent, through the subject's last visit. All AEs are to be reported using the CRF.

AEs (serious and non-serious neurological or neuro-developmental) should be recorded on the CRF through the subject's last visit.

8.3. Definition of an Adverse Event

In this study, an AE is any untoward medical occurrence in an infant exposed to study drug via maternal exposure in the parent study; the event need not necessarily have a causal relationship with the treatment or usage.

A standard list of examples of AEs is shown below (not all of these examples are applicable to this protocol):

- Abnormal test findings;
- Clinically significant symptoms and signs;
- Changes in physical examination findings;
- Hypersensitivity;
- Progression/worsening of underlying disease;
- Drug abuse;
- Drug dependency;

Additionally, they may include the signs or symptoms resulting from:

- Drug overdose;
- Drug withdrawal;
- Drug misuse;
- Drug interactions;
- Extravasation;
- Exposure during pregnancy (EDP);
- Exposure via breastfeeding;
- Medication error;
- Occupational exposure.

8.4. Medication Errors

This section is not applicable as no study medication is administered during this study.

8.5. Abnormal Test Findings

The criteria for determining whether an abnormal objective test finding should be reported as an AE are as follows:

- Test result is associated with accompanying symptoms, and/or
- Test result requires additional diagnostic testing or medical/surgical intervention; and/or
- Test result leads to significant additional concomitant drug treatment, or other therapy; and/or
- Test result is considered to be a relevant AE by the investigator or sponsor.

Merely repeating an abnormal test, in the absence of any of the above conditions, does not constitute an AE. Any abnormal test result that is determined to be an error does not require reporting as an AE.

8.6. Serious Adverse Events

A serious adverse event is any untoward medical occurrence at any dose that:

- Results in death;

- Is life-threatening (immediate risk of death);
- Requires inpatient hospitalization or prolongation of existing hospitalization;
- Results in persistent or significant disability/incapacity (substantial disruption of the ability to conduct normal life functions);
- Results in congenital anomaly/birth defect.

Medical and scientific judgment is exercised in determining whether an event is an important medical event. An important medical event may not be immediately life threatening and/or result in death or hospitalization. However, if it is determined that the event may jeopardize the subject or may require intervention to prevent one of the other AE outcomes, the important medical event should be reported as serious.

Examples of such events are intensive treatment in an emergency room or at home for allergic bronchospasm; blood dyscrasias or convulsions that do not result in hospitalization; or development of drug dependency or drug abuse.

8.6.1. Protocol-Specified Serious Adverse Events

There are no protocol-specified SAEs in this study. All SAEs will be reported by the investigator as described in previous sections, and will be handled as SAEs in the safety database (see the section on [Serious Adverse Event Reporting Requirements](#)).

8.6.2. Potential Cases of Drug-Induced Liver Injury

This section is not applicable as no study medication is administered during this study.

8.7. Hospitalization

Hospitalization is defined as any initial admission (even less than 24 hours) in a hospital or equivalent healthcare facility or any prolongation of an existing admission. Admission also includes transfer within the hospital to an acute/intensive care unit (eg, from the psychiatric wing to a medical floor, medical floor to a coronary care unit, or neurological floor to a tuberculosis unit). An emergency room visit does not necessarily constitute a hospitalization; however the event leading to the emergency room visit should be assessed for medical importance.

Hospitalization does not include the following:

- Respite care (eg, caregiver relief);
- Skilled nursing facilities;
- Same day surgeries (as outpatient/same day/ambulatory procedures).

Hospitalization or prolongation of hospitalization in the absence of a precipitating, clinical AE is not in itself an SAE. Examples include:

- Admission for treatment of a preexisting condition not associated with the development of a new AE or with a worsening of the preexisting condition (eg, for workup of persistent pretreatment laboratory abnormality);
- Social admission (eg, subject has no place to sleep);
- Administrative admission (eg, for yearly physical examination);
- Protocol-specified admission during a study (eg, for a procedure required by the study protocol);
- Optional admission not associated with a precipitating clinical AE (eg, for elective cosmetic surgery);
- Hospitalization for observation without a medical AE;
- Preplanned treatments or surgical procedures. These should be noted in the baseline documentation for the entire protocol and/or for the individual subject.

Diagnostic and therapeutic noninvasive and invasive procedures, such as surgery, should not be reported as AEs. However, the medical condition for which the procedure was performed should be reported if it meets the definition of an AE. For example, an acute appendicitis that begins during the AE reporting period should be reported as the AE, and the resulting appendectomy should be recorded as treatment of the AE.

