3.4. Baseline Variables

Baseline variables are those collected at the initial visit.

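### Section 8.7 keeps treatment-trial exemptions for preexisting conditions and preplanned procedures that conflict with the AE definition in Section 8.3, so some admissions for possible exposure outcomes can go unreported as SAEs

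*Protocol*

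**What the plan says.** Protocol Section 8.7 governs its exemptions with one sentence: "Hospitalization or prolongation of hospitalization in the absence of a precipitating, clinical AE is not in itself an SAE". Two of the examples under it matter here. The first is "Admission for treatment of a preexisting condition not associated with the development of a new AE or with a worsening of the preexisting condition", illustrated by an admission "for workup of persistent pretreatment laboratory abnormality". The second is "Preplanned treatments or surgical procedures. These should be noted in the baseline documentation for the entire protocol and/or for the individual subject". Neither preexisting nor preplanned is tied to a date. The section then says that the condition behind a procedure is reportable if it is an AE, but its worked example is an appendicitis with onset inside the reporting period.

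The surrounding rules are:

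- **Section 8.3:** "an AE is any untoward medical occurrence in an infant exposed to study drug via maternal exposure in the parent study". There is no requirement that onset follow consent.
- **Section 8.1:** "Non-serious, non-neurological AEs will not be collected". For a non-neurological event, seriousness therefore decides whether it is collected.
- **Section 8.2:** SAE reporting runs from informed consent to the last visit.
- **Sections 4 and 6.2.1:** the mother can be invited once the pregnancy or exposure is known. Visit 1 can fall anywhere from birth to 2 months of age.
- **SAP 3.5.1:** no treatment-emergent distinction is made, because no study drug is given to the infants.

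**The concern.** The exemptions come from trials in which a patient is observed, then treated, and conditions seen beforehand are set aside because the drug could not have caused them. This cohort has no such sequence. Exposure is at conception or in utero (Protocol Section 3), and no treatment is given in the study (Section 5). A condition present at birth or at enrolment may therefore be an outcome of exposure.

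Section 8.3 was adapted to this and Section 8.7 was not. Several neighbouring sections (8.4, 8.6.2, 8.11) are marked not applicable because no study medication is administered, and SAP 3.5.1 follows the same reasoning. Section 8.7 brings a before-and-after distinction back at the point of reporting, upstream of any table.

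At stake are the SAE listings (SAP 6.6) and the commitment in Section 2.1 to report all observed or volunteered SAEs. Capture could also differ between infants according to when their mothers consented.

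**Working it through.** The documents give no figure on this point, so the check is mainly a comparison of rules.

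**Step 1. What could preexisting refer to?**

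- *Before exposure.* The pretreatment example in Section 8.7 points this way. The infant has no observed pre-exposure period, so the exemption would have nothing to apply to.
- *Before consent or the first visit.* The reference to baseline documentation and the onset wording of the appendicitis example point this way. SAP 3.4 uses a similar notion: "Baseline variables are those collected at the initial visit". That sentence concerns variables and not AE rules, so it is only suggestive. On this reading, anything arising up to about 2 months of age could be set aside.

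The text does not choose between these readings.

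**Step 2. One illustrative history under both sections.** Take a non-neurological, non-congenital condition that appears at 2 weeks of age, stays stable, and leads to an inpatient admission at 4 months. No other seriousness criterion is met. (These ages are assumed.)

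| | Consent before birth | Consent at 6 weeks |
|---|---|---|
| Onset relative to the reporting period (8.2) | Inside | Before |
| AE under 8.3? | Yes | Yes |
| Can it be read as preexisting under 8.7? | No, if the reference date is consent | Yes |
| Admission at 4 months | SAE | Can be treated as not an SAE |
| If not an SAE, collected under 8.1? | Does not arise | No, unless Appendix 4 prompts a report |

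In the right-hand column, Section 8.3 supplies a precipitating AE while Section 8.7 offers the same admission as an example of having none. Both cannot hold for the same infant. The admission itself falls after consent in both columns, so the reporting-period start date alone does not explain the difference.

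**Step 3. What stays captured.** The exemption removes only the hospitalization criterion. Under Section 8.6, death, life-threatening events, persistent or significant disability, congenital anomaly and important medical events remain SAEs. New or worsening conditions are outside the exemption. Section 8.1 and Appendix 4 keep neurological and neuro-developmental events reportable, at least as non-serious AEs. For other non-serious events, Appendix 4 only encourages reporting when the event may be considered related to tanezumab exposure.

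**Step 4. Scale.** Section 9 expects fewer than 20 eligible infants, so at most 19:

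- One infant as a share of the cohort: 1/19 = 5.3% or more.
- One infant in a treatment arm of 5 (an assumed size, not in the documents): 1/5 = 20%.

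These show the weight of one infant. They equal the change in the SAE proportion only if that infant has no other counted SAE.

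**The case against.** The strongest reply is that the Section 8.7 bullets are only examples under the governing sentence. Read with Section 8.3, a condition present at enrolment is already an AE, so an admission for it does have a precipitating AE and the exemption never applies. The section's own sentence on the condition behind a procedure supports this. It is a coherent reading, and an investigator who adopts it loses nothing. But the bullets, the pretreatment illustration and the onset wording point the other way, and nothing tells the investigator which reading to follow.

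A second reply is that little of interest escapes. Neurological findings, which are the study's focus, remain reportable. Appendix 4 recommends reporting when the investigator is unsure whether an event is neurological. Section 8.1 lets the sponsor upgrade a non-serious AE. Delivery complications, outside healthcare reports and narratives also hold information (Sections 6.2.1.1, 7 and 9.4). This stands, and it narrows the gap considerably. However, these sources do not feed the SAE count, and the sponsor can upgrade only an event that was reported to it.

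A third reply is that consent may precede birth, in which case little can be called preexisting. That is possible under Section 4 but not required.

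A reader might infer that admissions for conditions present at enrolment are simply not reported as SAEs. The documents do not support that: most serious outcomes keep an independent route through Section 8.6, and Section 8.3 itself argues for reporting.

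**Conclusion.** The conflict between Sections 8.7 and 8.3 is real and should be resolved, but its reach is limited. An admission after consent can go unreported as an SAE when three conditions hold together: the underlying condition arose before consent, it is stable, and hospitalization is the only seriousness criterion met. If the condition is also non-neurological, it may not be collected as an AE. If it is neurological, it is still captured, but possibly only as non-serious.

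The number of affected infants cannot be estimated, because consent timing relative to birth is not fixed and no admission rates are given. The 5.3% figure rests on the ceiling of 19 infants and is a measure of scale, not a predicted undercount. The conclusion assumes that investigators may read preexisting as meaning before consent or before the first visit; the text permits that reading but does not compel it.

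**What to change.** Add one statement to Section 8.7, for example: *Because exposure precedes birth, a condition of the infant that is present at birth or at enrolment is an adverse event under Section 8.3 and is not preexisting for the purposes of these exemptions, including the exemption for preplanned procedures. An inpatient admission for such a condition after consent is assessed against the SAE criteria.*

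Revise the appendicitis example so that its onset wording does not imply that conditions beginning before consent fall outside AE reporting, and cross-refer to Section 8.2. Remove or replace the pretreatment illustration.

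The social, administrative and protocol-specified exemptions can stay. So can the bullets on optional admission and observation, since both apply only where there is no AE. A blanket rule that every medical admission is an SAE is not needed.

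The cost is a short protocol amendment and a few additional SAE reports, including some for minor planned admissions. Same-day surgery remains outside the Section 8.7 definition of hospitalization, which limits that number. No change to the SAP analyses is required.
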